Main and Secondary Outcomes: The main outcome of this study will be any condomless anal or vaginal sex with any sex partner at three weeks and three months following the video. Individuals who do not reply to the three week message will receive a second message at four weeks. Secondary outcomes include cost, self-efficacy, and other behavioral variables (Appendix 2).

Eligibility and Recruitment: Participants will be recruited through a banner link on a popular MSM web portal home page and an announcement sent to registered users by email and other social media platforms. Interested participants who click on the link will then be directed to the survey with a description of its contents and an online informed consent form. The survey is voluntary and to be eligible, participants must state that they were born biologically male or are transgender, had anal sex with men at least once during their lifetime, have had condomless anal/vaginal sex in the past three months, and are at least 16 years of age. All participants must provide their cell mobile number. Individuals identified by their cell phone number who enter the study twice and watch different videos will be excluded. No names or addresses will be collected from participants. All individuals who enroll in the study and reply to the text message will receive a 100 RMB (8.50 USD) pre-paid cell phone card for their time at the first FU and a 50 RMB pre-paid card for the second FU.

Measures: Survey items on socio-demographics and sexual behaviors will be collected using standardized survey instruments immediately before video watching, three weeks after video watching, and three months after video watching. Socio-demographic characteristics include participants' age, highest level of education completed, annual income, marital status, sexual orientation, and sexual orientation disclosure. Behavioral variables include number of sex acts in the past three weeks, condomless sex with men, condomless sex with women, condom self-efficacy, and other secondary outcomes specified in Appendix 2.

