Statistical Analysis: The primary outcome will be condomless vaginal or anal sex (with any sex partner) among MSM and transgender individuals following the assigned video intervention. Participants will be asked about using condoms all the time or not using condoms all the time since watching the video (individuals who have not had sex in the interval will be classified as no condomless sex). Condomless vaginal or anal sex includes condomless sex of any frequency (e.g., always condomless sex, occasional condomless sex, etc.). We will examine the non-inferiority hypothesis comparing the two interventions, as well as the superiority hypothesis. The difference in proportions having condomless sex (crowdsourced – social marketing) will be estimated, with a corresponding two-sided 95% Wald confidence interval. The crowdsourced intervention will be declared non-inferior to social marketing if the upper confidence limit is below 10%. If the upper confidence bound is below 0%, then the crowdsourced intervention will be declared superior to social marketing.

Our secondary outcomes are condom use self-efficacy, cost, and related behavioral outcomes. The objective of the cost analysis will be to estimate the total and incremental unit cost in using

video interventions to promote condom use. In this step, we will further collect cost related data from all the organizations involved in making condom use promotion videos. Detailed information that we will collect from these organizations is listed in Appendix 2. One of our secondary analyses will focus on those individuals who reported sex following the video intervention (excluding those who did not have sex in the interval between the video and the survey).

Missing Data Plan: Missing data in the primary outcome that accounts for <11% of participants will not be imputed and the complete-case approach will be used. However, in cases where missing data for the primary outcome is 11 to <20% of the total outcome, a sensitivity analysis using multiple imputation based on the PROC MI procedure in SAS (Cary, NC) will be used. If missing data accounts for \geq 20% of participants then we will use multiple imputation in the primary analysis.

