Effect modification analyses: Effect modification analyses will be undertaken based on prior exposure to condom promotion video watching to assess whether this exposure differs between the baseline groups. A linear probability model will be used to evaluate effect modification by testing for an interaction between intervention and prior video watching (e.g.,

 $Prob(Condomless Sex = 1 | Arm, AgeGrp) = \alpha + \beta_1 Arm + \beta_2 AgeGrp + \beta_3 Arm * AgeGrp).$ This model can be fit with the GENMOD procedure in SAS using the binomial distribution and identity link. If this model does not converge, then log-binomial regression will be used to estimate relative risks. *Secondary analysis:* We will examine the subset of individuals who reported sex during the follow-up period (3 weeks and 3 months respectively) and use causal inference methods to account for post-randomization selection bias. We will compare the proportion of individuals who have any sex between the two arms to determine if the intervention results in less frequent sex.

Sample size calculation: To calculate sample size we assumed an equal probability of reported condomless sex in the crowdsourced video intervention and social marketing intervention arms. We calculated the sample size for this binary outcome non-inferiority trial using the formula below with a one-sided significance level (α) of 2.5% and power (1- β) of 90%.²¹ Assuming a 50% probability of condomless sex in each arm, a non-inferiority limit of 10%, and loss to follow-up of 10%, a total sample size of 1170 individuals is required (585 in each arm). The sample size calculation was made using the formula:

$$n = f(\alpha, \beta) \frac{[\pi_s (1 - \pi_s) + \pi_e (1 - \pi_e)]}{(\pi_s - \pi_e - d)^2}$$

where π_s and π_e are the true probability of reported condomless sex in the social marketing intervention and crowdsourced video (experimental) intervention groups, respectively, d is the non-inferiority limit, and $f(\alpha, \beta) = [\Phi^{-1}(\alpha) + \Phi^{-1}(\beta)]^2$, where Φ^{-1} represents the cumulative distribution function of the standard normal distribution.

Sample size calculations for 90% power and a one-sided 0.025 significance level

| Probability | Probability | Non- | Probability of | Ν | Total |
|-------------|-------------|------------|-----------------------|---------|----------|
| of primary | of primary | inferiorit | loss to follow- | evaluab | sample |

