| outcome in | outcome in | y limit | up £ | le per | size for |

| control group [*] | experimenta l group [*] | | | arm | RCT |
|-------------------------------|-------------------------------------|-----|-----|-----|------|
| 0.50 | 0.50 | 0.1 | 0.1 | 526 | 1170 |
| 0.45 | 0.45 | 0.1 | 0.1 | 521 | 1158 |
| 0.40 | 0.40 | 0.1 | 0.1 | 505 | 1122 |
| 0.35 | 0.35 | 0.1 | 0.1 | 479 | 1064 |
| 0.30 | 0.30 | 0.1 | 0.1 | 442 | 982 |

Note: *Based on the pilot study, 9/25 (95% confidence interval: 18% to 57%) had condomless sex at least once in the three week period immediately following the video intervention. \pounds According to one similar RCT we conducted at 2014, the lost to follow up rate was about 10%; adjustment for loss: required evaluable N per arm/(1-loss to follow up).

Ethical review: IRB approval will obtained from the following institutional ethical review boards

prior to study enrollment - Guangdong Provincial Center for Skin Diseases and STI Control,

University of North Carolina at Chapel Hill, and University of California San Francisco.

Trial registration: This trial was registered in ClinicalTrials.gov (NCT02516930).

References

3. Ministry of Health People's Republic of China. 2012 China AIDS Response Progress Report. Beijing2012.

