| norms | levels of social norms when comparing their pre-intervention | | |
| | and post-intervention condom use norms* | | |
| Condom self-efficacy | Frequency of men, defined as number of men who had an | | |
| | increase in self-efficacy when comparing their pre-intervention | | |
| | and post-intervention self-efficacy** | | |
| Condom negotiation | Frequency of men, defined as the number of men who attempted | | |
| | to convince an unwilling partner to use a condom immediately | | |
| | following the video intervention divided by the total number of | | |
| | men who viewed the video in that arm | | |
| HIV testing | Frequency of men, defined as the number of men who reported | | |
| | being tested for HIV during the interval between watching the | | |
| | video and following up compared to the number of men who | | |
| | followed up | | |
| STI testing | Frequency of men, defined as the number of men who reported | | |
| | being tested for STIs (excluding HIV) during the interval | | |
| | between watching the video and following up compared to the | | |
| | number of men who followed up | | |

*Condom use social norms will be measured using six survey items that are each on a five point Likert scale. Increased condom use social norms will be defined as having an increase from baseline in any two of these six survey items and dichotomized accordingly. The condom use social norm outcome will be assessed in the entire group as well as the subgroup of men who were referred by their friends.

**Self-efficacy will be measured using seven survey items that are each on a five point Likert scale. Increased self-efficacy will be defined as having an increase from baseline in any two of these seven survey items and dichotomized accordingly. The self-efficacy outcome will be assessed in the entire group as well as the subgroup of men who were referred by their friends.

| | Financial costs | Economic costs |
|--|--|--|
| Phase | | |
| Contest development | Inputs to be captured, can all directly be found in the project financial accounts, main challenge is to allocate across components and to allocate SESH overhead costs | Extra inputs not already captured by financial costs |

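### The three-month outcome includes the first three weeks, but no rule links the two surveys, so literal complete-case analysis sets aside events already reported

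*Protocol*

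**What the plan says.** Protocol section 5, Main and Secondary Outcomes, sets the main outcome as any condomless anal or vaginal sex "with any sex partner at three weeks and three months following the video". Under Statistical Analysis the question put to participants is cumulative: "Participants will be asked about using condoms all the time or not using condoms all the time since watching the video". The same section analyses the difference in proportions with a two-sided 95% Wald interval and declares non-inferiority if the upper limit is below 10%.

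The Missing Data Plan has three bands. In the lowest, "Missing data in the primary outcome that accounts for <11% of participants will not be imputed and the complete-case approach will be used". From 11% to below 20%, multiple imputation is a sensitivity analysis. At 20% or more, it becomes the primary analysis.

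The protocol does not say how a three-week answer bears on three-month status, which answer prevails if the two conflict, or whether a man with a reported three-week event and no three-month reply counts as missing.

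**The concern.** The three-month window contains the three-week window, so the two answers are logically tied. A true *yes* at three weeks fixes the three-month outcome as *yes*. Two problems follow if the written rules are applied as they stand.

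- A man who reported an event at three weeks and then does not reply has no three-month answer, so the complete-case rule removes him. His outcome is known, not missing.
- A man may say *yes* at three weeks and *always used condoms* at three months. He is then an event and a non-event for the same weeks.

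The stake is the three-month non-inferiority conclusion. Complete-case analysis is biased if loss depends on the three-week answer, and data already collected would remove most of that bias.

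**Working it through.** **1. The plan's own figure.** Section 5 gives 50% in each arm, a 10% margin, one-sided 2.5%, 90% power and 10% loss. f = (1.960 + 1.2816)² = 10.507. n = 10.507 × (0.25 + 0.25) / 0.10² = 525.4, so 526 evaluable per arm. 526 / 0.9 = 584.4, so 585 per arm and 1170 in total. This matches the protocol. The present point does not change it.

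**2. Assumed inputs.** The protocol gives no three-month event rate and no three-month loss. Its pilot gives 9/25 = 36% at three weeks, and its only loss figure is about 10%. I assume 36% by three weeks and 60% by three months in the social marketing arm, 90% three-week response, and 15% three-month loss.

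**3. Known events set aside.**
- Lost per arm: 585 × 0.15 = 87.75. Known events among them: 87.75 × 0.90 × 0.36 = 28.4.
- Truly undetermined: (87.75 − 28.4) / 585 = 10.1%, against 15% by non-response.
- At the protocol's 10% loss: 58.5 × 0.90 × 0.36 = 19 men. Undetermined: (58.5 − 19) / 585 = 6.8%.
- Upper bound at 10% loss, if every man lost had answered at three weeks: 58.5 × 0.36 = 21, or 58.5 × 0.50 = 29.

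**4. Effect on the non-inferiority decision.** Take a true three-month difference exactly at the margin: crowdsourced 42% then 70%, social marketing 36% then 60%. Three-week positives are lost at rate L where stated, and everyone else at 15%. In an arm with three-week rate p3 and three-month rate p, the complete-case proportion is

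[p3(1 − L) + (p − p3)(0.85)] / [p3(1 − L) + (1 − p3)(0.85)].

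Example, crowdsourced arm, L = 20%: (0.336 + 0.238) / 0.829 = 0.692. The difference is 0.692 − 0.600 = 9.2 points. The Wald standard error with 485 and 497 men is 0.0304. The chance of declaring non-inferiority is Φ[(0.100 − 0.0924)/0.0304 − 1.96] = 4.4%.

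| Excess loss of three-week positives (L = 20 / 25 / 30%) | Complete-case difference, points | False non-inferiority |
|---|---|---|
| Crowdsourced arm only | 9.2 / 8.4 / 7.6 | 4.4 / 7.3 / 11.8% |
| Both arms | 10.1 / 10.2 / 10.3 | 2.3 / 2.1 / 2.0% |
| Social marketing arm only | 10.9 / 11.8 / 12.7 | 1.2 / 0.6 / 0.2% |

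Overall loss in the first row is 16.0%, 17.1% and 18.1%, so complete cases stay primary and imputation is a sensitivity analysis. In the second row at L = 30% it is 20.9%, which would already make imputation primary.

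**5. The same scenarios using both surveys.** I simulated maximum likelihood with three states per man (event by three weeks, first event later, none), with the interval taken from the empirical SD. False non-inferiority is about 2.6–3.3% in the first row and 2.2–2.5% in the other two. The remainder comes from men who missed the three-week survey.

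**6. Loss unrelated to outcome, no true difference, 60% in each arm.** Complete cases: SD = √(2 × 0.24 / 497.25) = 0.0311, power 89.6%. Maximum likelihood on both surveys: SD about 0.0302, power about 91.2%. A two-step life-table estimate, p3 + (1 − p3)h with h = 0.24/0.64 = 0.375, has per-arm variance 0.625² × 0.36 × 0.64 / 526.5 + 0.64² × 0.375 × 0.625 / (526.5 × 0.64 × 0.85) = 0.000506. That gives SD 0.0318 and power about 88%, slightly worse than complete cases.

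**7. Contradictory answers.** Suppose 2% to 10% of three-week positives say *no* at three months. That is 526 × 0.36 × 0.02 = 4 to 526 × 0.50 × 0.10 = 26 men per 526, and the three-month proportion is understated by 0.7 to 5.0 points. In the scenario of step 4 with no excess loss and a 10% contradiction rate in both arms, the proportions are 0.658 and 0.564, the difference is 9.4 points, and false non-inferiority is Φ(0.006/0.0308 − 1.96) = 3.9%.

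**The case against.** **The text never says that each survey is analysed alone or that known events are dropped.** A reader might infer both. The documents do not support them as statements of the plan, because a man with a recorded event need not be missing under the protocol's wording, and a statistical analysis plan could define the derivation. This stands, and it limits the point to what follows if the written rules are applied literally. The complete-case rule and its thresholds are, however, fixed in the protocol itself.

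**The error inflation needs one-sided loss.** A reader might infer that the rule makes non-inferiority too easy. That holds only if three-week positives drop out more in the crowdsourced arm. The same excess in both arms is slightly conservative, and excess in the other arm is strongly so. The protocol gives no reason to expect either arm to lose more.

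**The planned sensitivity imputation already applies at 16–18% loss.** It does, but it is not primary. As written, nothing prevents it from imputing *no* to a man who has already reported an event.

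**Recounting missingness would help.** A reader might want known events left out of the 11% and 20% counts. At 15% loss the count would fall to about 10% and the planned sensitivity imputation would be switched off, so that change should not be made.

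**Three months is the lesser time point.** The Summary frames the hypothesis at three to four weeks, with three months as an additional follow-up. This stands. At three weeks, only men who missed that survey and later report none could be recovered.

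**HIV and STI testing.** A reader might extend the point to these outcomes, since Appendix 2 counts men "being tested for HIV during the interval between watching the" video and follow-up. Its denominator is men who followed up. That does not exclude a man who answered only at three weeks, so no dropping of known tests is shown.

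**Conclusion.** The point holds in limited form. The protocol defines a cumulative outcome at two nested times, keeps complete cases as primary below 20% missing, and leaves the link between the answers undefined. Read literally, it discards known three-month outcomes (about 19 men per arm at 10% loss, about 28 at 15%) and allows contradictory records.

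The effect on the three-month decision is not in one fixed direction: false non-inferiority ranges from about 0.2% to 12%, depending on which arm loses its three-week positives. If loss is unrelated to outcome, the gain from using both surveys is only a modest rise in power. Every figure beyond the sample size rests on assumed rates. The sample size is unaffected and the three-week result barely so. The change is worth making because a better analysis is available from data the trial will already hold.

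**What to change.** - State that the three-month outcome is cumulative from the video, and that a *yes* at either survey counts. A later *always* then does not cancel an earlier *yes*.
- For the three-month analysis, at any level of missingness, replace complete cases by multiple imputation or maximum likelihood, by arm, using the other survey's answer and imposing that *yes* at three weeks implies *yes* at three months. The 10% margin and the upper-limit rule stay as they are.
- Do not simply add the recovered men to the complete cases. They are all events, so this would push the proportion upward.
- Keep the 11% and 20% triggers on survey non-response, so that no planned imputation is lost.
- Report the complete-case Wald analysis at three months as a sensitivity analysis.
- Do not use the two-step life-table estimate as an equivalent, since it loses some precision.

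The cost is some wording and a little programming, with no new data or participants. The analysis becomes slightly more complex, and men who answer both surveys have two chances to report an event. The report should say so.

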Appendix 1. Overview of MSM web platforms and screen shots.

We will partner with the largest CBO, Danlan. This CBO provides sexual health services such as HIV and syphilis rapid testing and counseling, as well as linkage to care (accompaniment to clinical services for infected individuals). To engage MSM in health-seeking behaviors, the CBO also maintains a web platform where MSM can participate in sexual health forums, find out about LGBT-related events, and catch up on news stories concerning LGBT communities. These web platforms also serve as portals to other websites of interest to MSM, such as social networking sites WeiBo and BF99, movie databases, and gay mobile app sites like Blued and Jack'd.

Figure 1. Screenshots of the MSM web portal in Beijing, Danlan Gongyi.

| Appendix 2. Sec | ondary outcomes | measured as | part of this RCT. |
|------------------|-----------------|-------------|-------------------|
| rippondin 2. Dec | ondary outcomes | mousureaus | pure or end recre |

| Secondary Outcome | Definition | | |
|-----------------------|--|--|--|
| Incremental cost | Incremental cost, defined as the cost associated with respective | | |
| | video interventions (development, start-up, implementation, | | |
| | condom use, intervention – see Table 1 below for details) per | | |
| | individual who reported no sex or sex with a condom during the | | |
| | follow-up period. | | |
| Female condomless | Frequency of men, defined as number of men who reported | | |
| sex | condomless vaginal or anal sex with a woman divided by the | | |
| | total number of men who viewed the video in that arm. | | |
| Male condomless sex | Frequency of men, defined as number of men who reported | | |
| | condomless anal sex with a man divided by the total number of | | |
| | men who viewed the video in that arm | | |
| Post-video condomless | Frequency of men, defined as number of men who reported | | |
| sex | condomless vaginal or anal sex with any partner immediately | | |
| | following the video intervention divided by the total number of | | |
| | men who viewed the video in that arm | | |
| Frequency of sex acts | Frequency of men, defined as the number of men who had | | |
| | decreased total number of sex acts in the three weeks following | | |
| | the intervention compared to the three weeks immediately | | |
| | preceding the intervention in that arm | | |
| Condom use social | Frequency of men, defined as number of men who report higher | | |

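### Whether the intervention makes sex less frequent is to be judged from the proportion with any sex, which measures abstinence and cannot show fewer acts among those still having sex

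*Protocol*

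**What the plan says.** Under Secondary analysis, within the Effect modification analyses paragraph of section 5, the protocol plans an analysis of the subset who reported sex during follow-up, at three weeks and at three months. It will "use causal inference methods to account for post-randomization selection bias". The next sentence reads: "We will compare the proportion of individuals who have any sex between the two arms to determine if the intervention results in less frequent sex".

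Two other places bear on frequency:

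- The Measures paragraph of section 5 collects act counts: "Behavioral variables include number of sex acts in the past three weeks". The survey is given before the video, at three weeks and at three months.
- Appendix 2 lists Frequency of sex acts as a secondary outcome. It is the number of men with a "decreased total number of sex acts in the three weeks following" the video, relative to the three weeks before it.

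The Secondary analysis text does not mention the Appendix 2 outcome. The Statistical Analysis paragraph classifies participants with no sex in the interval as having had no condomless sex.

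**The concern.** The question is about frequency, but the measure is whether a participant had at least one act. The null hypothesis being tested is equal P(acts ≥ 1) in the two arms. That is a statement about abstaining. A participant who goes from many acts to few contributes the same value before and after.

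This matters for reading the primary result. The primary outcome combines condom use with sexual activity: a participant can avoid condomless sex by using condoms, by abstaining, or by having fewer occasions on which a condom might be omitted. The any-sex comparison addresses the second route and not the third. If it showed no difference, and the protocol's sentence were followed, the third route would be dismissed without having been examined, and an arm difference might be credited to condom use.

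Enrolment adds to the problem. Participants must "have had condomless anal/vaginal sex in the past three months", so many will probably have sex again, above all over a three-month interval. The any-sex proportion may then lie close to its ceiling.

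**Working it through.** **1. Sample size.** The protocol gives no power figure for the any-sex comparison, so the only stated figure to reproduce is the primary one. With one-sided 2.5%, power 90%, 50% in each arm and a 10% limit, n = (1.960 + 1.282)² × (0.25 + 0.25) / 0.10² = 525.4, that is 526 evaluable per arm. Then 526/0.9 rounds up to 585 per arm, 1170 in total. This agrees with the protocol, and 526 per arm is used below.

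**2. Fewer acts among those who remain active.** Nobody moves to zero, so P(acts ≥ 1) is equal in the two arms and the comparison rejects at its error rate, 5%. This needs no distributional assumption. Simulation (400 runs per scenario; Poisson or negative binomial with dispersion parameter 1; mean 1 to 6 acts per three weeks; falls of 20%, 30% and 50%) gave rejection rates of 0.01 to 0.07 for any-sex and 0.71 to 1.00 for a t-test on the counts.

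**3. A proportional fall in everyone.** Assumed, because the protocol gives no act distribution: negative-binomial counts with shape k of 0.7, 1 or 2; mean μ of 2 to 4 acts in three weeks or 8 to 12 in three months; two-sided 5%.

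- Any-sex: p(μ) = 1 − (k/(k+μ))^k. Power ≈ Φ(|p₁ − p₂|/SE − 1.96), with SE² = [p₁(1−p₁) + p₂(1−p₂)]/526.
- Ratio of means: SE² of the log ratio = [(1/μ₁ + 1/k) + (1/μ₂ + 1/k)]/526. Power ≈ Φ(|ln(μ₂/μ₁)|/SE − 1.96).

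Worked case: k = 1, mean 3 falling by 20% to 2.4.

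- Any-sex: p₁ = 1 − 1/4 = 0.750 and p₂ = 1 − 1/3.4 = 0.706. SE = √[(0.1875 + 0.2076)/526] = 0.0274. The ratio is 0.0441/0.0274 = 1.61, so power = Φ(−0.35) = 0.36.
- Counts: SE = √[(1.333 + 1.417)/526] = 0.0723. The ratio is 0.2231/0.0723 = 3.09, so power = Φ(1.13) = 0.87.

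Over all the assumed shapes and means, the power of the any-sex comparison is:

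| Fall in mean acts | Three weeks (mean 2 to 4) | Three months (mean 8 to 12) |
|---|---|---|
| 20% | 0.26 to 0.57 | 0.16 to 0.24 |
| 25% | 0.41 to 0.79 | 0.24 to 0.38 |
| 30% | 0.58 to 0.93 | 0.35 to 0.55 |
| 50% | 0.99 or more | 0.90 to 0.99 |

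The assumed proportion with any sex before the fall is 61% to 89% at three weeks and 83% to 98% over three months. For a 20% fall at three weeks, the ratio of mean counts has power 0.73 to 0.98 by the formula (0.73 to 0.99 by simulation).

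**4. The Appendix 2 outcome.** In the simulations of step 2, extended to proportional falls, the share with fewer acts after than before had power 0.15 to 1.00 over both patterns. At a mean of 4 or more acts it was 0.79 to 1.00. It is weak when acts are few.

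**The case against.** The strongest reply is that frequency is handled elsewhere. Act counts are collected, and Appendix 2 pre-specifies an outcome on them. A reader might infer from the Secondary analysis sentence that the plan has no other analysis of frequency; that is wrong. What remains is that the sentence still assigns the frequency conclusion to the any-sex comparison without pointing to Appendix 2, and nothing says which governs if they disagree. The Appendix 2 outcome is also reduced to decreased or not, and is defined at three weeks only.

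Second, the sentence follows directly on the subset analysis, where comparing any-sex proportions is a sensible check on selection. Appendix 2 also uses frequency to mean a number of men, so less frequent could be read as fewer men reporting sex. The comparison does deserve to stay. But the same appendix uses a number of acts for its outcome on frequency of sex, so the wording is at best ambiguous and should be settled.

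Third, the rule counting no sex as no condomless sex works through abstinence, which any-sex does measure. That is correct for that route. It leaves out fewer occasions among those who remain active.

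Fourth, a reader might infer that a real fall in frequency would usually be reported as no difference, or that a drop from eight acts to four would go unseen. The documents do not support this. For a proportional fall from a mean of 8 to 4, power is 0.95 to 0.99 under the assumed shapes. In the second set of scenarios (Poisson or negative binomial, mean 1 to 6), power was below 0.50 in 5 of 24 scenarios with a proportional fall, all with a 20% fall. A halving is invisible only if nobody moves to zero.

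**Conclusion.** The measure does not match the question put to it. The part that needs no assumption is that any-sex cannot register fewer acts among those who stay sexually active; there its power equals its error rate, about 5%. For a proportional fall, the loss is substantial for modest effects (a 20% fall: 0.26 to 0.57 at three weeks, against 0.73 or more for mean counts) and larger over three months (0.16 to 0.24). It is smaller or absent for large effects. These ranges rest on assumed negative-binomial counts and on 526 evaluable per arm; another act distribution would move them.

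The point concerns a secondary analysis and the explanation offered for the primary result. It does not touch the primary estimate, the 10% margin or the non-inferiority decision, and should not be read as doing so. It is worth correcting because the sentence fixes an inference that the measure cannot support.

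**What to change.** In the Secondary analysis text of section 5:

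1. Keep the any-sex comparison, and state that it describes abstinence and selection into the subset who reported sex.
2. Draw the frequency conclusion from the three-week act counts already collected: the between-arm ratio of mean acts with a 95% confidence interval, from a log-link or negative-binomial regression with robust variance, adjusted for the baseline three-week count.
3. Refer to the Appendix 2 outcome and report it alongside, making clear that the ratio of means carries the frequency conclusion.

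The cost is a change of wording and one extra regression, with no new data. Self-reported counts are skewed and noisy, which the robust variance addresses only in part. At three months the count covers the past three weeks and not the whole interval, so the conclusion there should be limited to that window.
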